### III. Preliminary Studies/Progress Report:

**Preliminary data to support the study concept: We have found testicular and cardiometabolic function are inversely related in pre-pubertal XXY boys, and androgen supplementation improves cardiometabolic markers.** In a study of 93 boys with XXY age 4-12 (NCT00348945), 20% had evidence of testicular failure (low INHB) at baseline, as well as elevated percent body fat (%BF, z-score +1) and high prevalence of metabolic syndrome features. Low INHB was associated with greater cardiometabolic risk including higher blood glucose, triglycerides, and low-density lipoprotein (LDL), and lower high-density lipoprotein (HDL), all  $p < 0.05$ . This is evidence that both testicular and cardiometabolic function is impaired before puberty in boys with XXY. Furthermore, two years of treatment with a weak androgen improved body composition (Figure 3) and cardiometabolic markers.

**Figure 3.** %BF is high in XXY boys 4-12 yrs old. Androgen therapy improves body composition ( $p=0.04$ ).

**Preliminary data to support the study design: Our pilot study suggests this regimen of T is well tolerated and does affect body composition.** In preparation for this study, I designed a feasibility study to evaluate the short-term effects of T on body composition (COMIRB 14-7240, NCT02408445) in infants. We enrolled 18 infants with XXY between 6-15 weeks of age and randomized subjects to receive testosterone cypionate 25mg intramuscularly every 4 weeks x 3 or no treatment. I hold an Investigational New Drug (IND 124260) file for the use of T in infants with XXY, and this file will be updated with this protocol. There have been no serious adverse events and the only side effects were an increase in appetite ( $n=2$ ) and acne ( $n=2$ ). %BF at baseline was normal, however increased by a z-score of  $+0.86 \pm 0.65$  over 12 weeks in infants not receiving T, while the change in %BF z-scores for infants who received T was  $-0.24 \pm 0.67$  (Figure 4). XXY infants who did not receive T had 4% more body fat at 5 months of age than normal male

**Figure 4. Left:** T shots favorably effect the change in %BF z-scores after 12 weeks in infants with XXY. **Right:** At 5 months (visit 2), %BF is 4% higher in XXY boys not treated with T compared to 316 healthy boys.

infants in the local Healthy Start Study.

**Preliminary data to support feasibility of recruitment: Our pilot study exceeded recruitment goals and allowed us to adapt our study design based on limitations.** We had excellent recruitment with an average one new subject per month and 100% retention rate without funds for recruitment or travel reimbursement. Informal focus groups and surveys have been conducted with parents to identify their reasons for or against participation. The greatest limitations in recruitment/retention have been 1) costs incurred due to travel to Denver and 2) unwillingness to participate in a trial where they may potentially be randomized to not receive T (as all perceived high benefits and low risks). After designing the current study, we surveyed 34 parents of XXY infants anonymously using a link posted on targeted social media groups. 67% reported they “definitely” would enroll their child if eligible in this study design, 21% said they “maybe” would enroll, and only 12% indicated they would not enroll. These pilot findings were critical in designing this study.

## IV. Research Methods

### A. Outcome Measure(s):

#### Primary for Specific Aim 1

Change in %BF z-scores from baseline to 12 weeks (per PeaPod)

#### Primary for Specific Aim 2

Change in motor composite percentile on the AIMS assessment from baseline to 12 weeks

#### Primary for Specific Aim 3

Change in C14:1 long chain acylcarnitine (LCAC) from baseline

**Secondary outcomes:** Change in %BF z-scores from 12 to 24 weeks; change in anthropometric measurements from baseline to 12 and 24 weeks; change in gross and fine motor scaled scores from the PDMS; cognitive and language scores on the Bayley; adaptive functioning from the ABAS; serum hormones, lipids, BCAA, LCAC, and pathway analysis of untargeted metabolomics; urine metabolites; and number and type of adverse events.

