### Specific Aim 1: To quantify the short-term effect of T in infants with XXY on cardiometabolic outcomes.

**Hypothesis:** Percent body fat (%BF) will follow a normal trajectory in treated infants, while infants not receiving T will have greater %BF. **Approach:** In the TESTO: Testosterone Effects on Short-Term Outcomes trial, infants with XXY (n=75) age 4-12 weeks will be randomized 1:1 to receive 25mg intramuscular T injections every 4 weeks for 3 doses or placebo. %BF will be assessed by air displacement plethysmography at baseline, 12 weeks, and 24 weeks. The primary outcome is change in %BF z-scores at 12 weeks between groups (powered to detect a difference of 0.5SD). Infants initially receiving placebo will get T in the second half of the study (12-24 weeks). Secondary outcomes include change %BF z-scores from 12-24 weeks, growth parameters, and serum leptin.

**Specific Aim 2: To quantify the short-term effects of T in infants with XXY on neurodevelopment, gonadal function and safety outcomes.**

**Hypothesis:** (1): XXY infants receiving T will have greater gains in standard scores on early motor skills, emerging language, and adaptive functioning. (2): T treatment will not impair gonadal function, as measured by gonadotropins and biomarkers of Sertoli cell function. (3): There will be no serious adverse outcomes associated with T treatment in infants with XXY. **Approach:** Infants from Aim 1 will be given standardized neurodevelopment assessments at baseline, 12 and 24 weeks. Serum hormone biomarkers of gonadal function will also be obtained at these times. Adverse events will be monitored throughout the study.

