- At the 2nd International Workshop on Klinefelter Syndrome (Germany, March 2016) the lack of randomized controlled trials of T in XXY, and the need for these studies to be conducted with patient-centered outcomes, was emphasized and nearly unanimously agreed upon by experts in KS.
- The field of metabolomics offers an opportunity to investigate the mechanisms of these changes.

The outcome measures chosen for this study are not only surrogate markers for future disease and disability, but are **meaningful patient-centered outcomes in infancy and childhood.**

- High body fat with poor muscle tone may limit an infant’s ability to engage with his environment.
- Delays in motor, language, and social development affect 75% of boys with XXY and strongly correlate with future cognition, behavior, and academic performance.
- This study will be the first to test the hypothetical mechanism demonstrated in animal models that T induces immediate metabolic and epigenetic modifications that in turn confer lifelong effects on metabolism and neurocognition.

[figure not shown]

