**F. Data Analysis Plan:**

The primary outcome for **specific aim 1** is the change in %BF z-scores between baseline and 12 weeks between treatment groups. Z-scores will be calculated using published norms for age, and the difference between groups will be assessed with a two-sided t-test using an alpha of 0.05. Allowing for a 10% drop-out rate, a sample size of 27 in each group gives us 80% power to detect a difference down to 0.5 z-score change between groups, and >99% power to detect the change score we observed in our pilot study (1.0 z-score change) assuming a variance of 0.65 per our pilot data. We will next use regression models with treatment group, baseline %BF, age of enrollment and feeding method as explanatory variables to assess absolute %BF at 12 weeks. Secondary analyses will include change in %BF z-scores from 12 to 24 weeks 1) in the group receiving T first (are the effects of T maintained or lost?) and 2) in the group receiving T second (does later T have the same effect?). We will analyze anthropometric measurements and serum biomarkers similarly.

For **specific aim 2**, the change in standard scores on developmental assessments will be analyzed in a similar fashion as in specific aim 1. Based on our pilot data, our sample size will yield 80% power to detect a difference between groups of 23 percentile points on the AIMS composite. Secondary analysis will include the changes in scaled scores for the individual Peabody domains and AIMS subtests, the Bayley composite scores, and the ABAS composite at 12 and 24 weeks. Gonadal function and safety outcomes will be compared between subjects on T and placebo using descriptive statistics.

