For **specific aim 3 (exploratory)**, we will compare C14:1 concentrations (an easily identified LCAC) between treatment groups at 12 weeks using two-sided t-tests, hypothesizing C14:1 will be lower in the T treated group (representing improvement in fatty acid oxidation and energy metabolism). This aim is exploratory; with 10 subjects per group we will have 80% power to detect a difference of 1.3 SD with a two-sided alpha of 0.05. Then, paired t-tests will be used to compare C14:1 before and after T treatment (5 paired samples), with similar power. We will analyze secondary outcomes including other LCAC and BCAA (leucine, isoleucine, and valine) in a similar fashion. Next, we will use principle component analysis on the entire dataset from the comprehensive untargeted analysis to identify patterns and pathways altered with T treatment. The spectra data file from the non-targeted metabolomics panel will be uploaded to MetaboAnalyst, and the software will be used for Metabolite Set Enrichment Analysis as well as Pathway Enrichment Analysis. We will have >80% power to detect at least 2-fold changes between T treated and untreated using a significance level of 0.0001 (less than two false positives based on the conservative Bonferroni correction for multiple comparisons). We will also input the analytes into known KEGG pathways of energy metabolism to look for pathway enrichment.

Table 2. Summary of primary and secondary outcome measures for each Specific Aim (SA).

SA	Primary Outcome	Weeks		Measurement Tool
		12	24	
SA 1: Cardiometabolic	Change %BF z-scores from baseline	X		PeaPod
	Secondary Outcomes			
	Change %BF z-scores from baseline		X	PeaPod
	Change in height, weight, weight-for-length and waist circumference z-scores from baseline	X	X	Physical exam measurements
	Serum leptin, lipids, and insulin	X	X	Immunoassays in CCTSI core laboratory
SA 2	Primary Outcome			

	Change in motor composite from baseline	X		AIMS percentile composite score (all domains)
	Secondary Outcomes			
	Serum LH, FSH, INHB, AMH, E2 and Total T	X	X	Immunoassay and LC/MS ([name] lab)
	Change in gross and fine motor scaled scores	X	X	Scaled scores on all PDMS-2 domains, AIMS
	Cognitive and Language composite scores	X	X	Bayley III: cognitive and language domains
	Adaptive functioning	X	X	ABAS III standard scores
	Number of adverse events	X	X	Verbal questionnaire, parent-report
SA 3: Metabo- Iomics	Primary Outcomes			

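### The Aim 2 primary tests change in AIMS percentile while its hypothesis and analysis text name standard scores, and the 23-point target has no stated SD and no constant meaning in SD units

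*Combined protocol and SAP*

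**What the plan says.** Section IV.A defines the Aim 2 primary as "Change in motor composite percentile on the AIMS assessment from baseline to 12 weeks". Table 2 in section IV.F also names the AIMS percentile composite, and the power statement is for "a difference between groups of 23 percentile points on the AIMS composite" at 80% power, citing pilot data without an SD.

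Two other places use a different scale. The Aim 2 hypothesis in section I predicts that "XXY infants receiving T will have greater gains in standard scores on early motor skills". The Aim 2 paragraph of section IV.F says "the change in standard scores on developmental assessments will be analyzed in a similar fashion" to Aim 1. The Aim 1 method is a two-sided t-test at 0.05 on change, followed by regression on treatment group, baseline value, age at enrolment and feeding method.

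The other scored outcomes use z-scores (%BF), scaled scores (PDMS-2), composite scores (Bayley) or standard scores (ABAS). No reason is given for using percentiles for the AIMS primary.

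**The concern.** The scale of a primary outcome should be stated once and consistently. Here an analyst could follow the outcome definition (percentile) or the hypothesis and analysis sentence (standard score), and the two can give different p-values on the same data.

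Percentile is also an awkward scale for change. It is bounded and compresses differences towards both ends, so the same motor gain yields fewer points for an infant who starts very low or very high than for one near the middle. Infants in the tails therefore carry less weight in the treatment contrast, and a target in percentile points has no fixed size in motor terms. Without the pilot SD, the reader cannot check the target either.

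**Working it through.** **Inputs.** From section IV.F: two-sided alpha 0.05, 80% power, 23 points, 27 per arm, 10% drop-out. From Figure 6: 30 per group. From section IV.B: 75 enrolled. The documents give no SD of AIMS change, baseline AIMS distribution or pre-post correlation, so these are assumed and varied below.

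**1. The plan's own figures.** The 27 per arm comes from Aim 1: 2 x (1.960 + 0.842)^2 x 0.65^2 / 0.5^2 = 26.5, rounded up to 27, reading 0.65 as an SD although the text calls it a variance. With drop-out, 27/0.90 = 30, which matches Figure 6.

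For Aim 2 the 23 points can only be inverted:

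- SD of change = 23 / [2.802 x sqrt(2/27)] = 23 / 0.763 = 30.2 points (normal approximation).
- With the t distribution the detectable standardized difference is 0.777, and 23/0.777 = 29.6.
- At 37.5 per arm (75 in total, no drop-out) the implied SD is 35.6 (normal) or 35.1 (t).

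These are plausible SDs for a percentile change, but the 23 points are neither reproduced nor refuted.

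**2. Percentile points against SD units.** With z = inverse-normal(percentile/100), 23 points from the 50th percentile is z(0.73) - z(0.50) = 0.61. From the 5th it is z(0.28) - z(0.05) = -0.58 + 1.64 = 1.06.

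| Starting percentile | Points gained for +0.6 SD | SD equivalent of +23 points |
|---|---|---|
| 2nd | 5.3 | 1.38 |
| 5th | 9.8 | 1.06 |
| 25th | 22.0 | 0.62 |
| 50th | 22.6 | 0.61 |
| 90th | 7.0 | not attainable |

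**3. Power lost to the scale alone.** This simulates 27 per arm with 20,000 trials per scenario. Z-scores are normal with unit SD, the treatment shift is constant in z, and the correlation is 0.3, 0.5 or 0.7. The shift is 0.777 x sqrt(2(1 - correlation)), so the t-test on change in z has 80% power. The same data are then tested as change in percentile.

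| Cohort mean (z) | Power on percentile change |
|---|---|
| 0 | 74-75% |
| -0.5 | 77-80% |
| -1 | 76-81% |
| -1.5 | 70-79% |
| -2 | 62-75% |

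The loss stays small over much of the range because compression shrinks the SD as well as the difference.

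**4. Where the cohort might sit.** In the same model the pooled SD of percentile change is 23-33 points at a mean of 0, 20-30 at -1, 17-26 at -1.5 and 13-20 at -2. The implied SD near 30 fits means from 0 to -1 and not -1.5 or -2.

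**5. Effect of baseline adjustment.** The SD of change is sqrt(2(1 - r)), and the residual SD after adjusting for baseline is sqrt(1 - r^2). The standardized effect therefore rises from 0.777 to 0.777 x sqrt(2/(1 + r)): 0.96, 0.90 and 0.84 for r = 0.3, 0.5 and 0.7. Simulated power on the z scale is about 84-93%.

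To separate the two sources, a further run (8,000 trials per scenario) at r = 0.5 and cohort mean 0 gave 74% for percentile change, 87% for percentile with baseline as covariate, and 89% for z with baseline as covariate. At a mean of -1 the sequence was 78%, 85%, 89%. At r = 0.7 and a mean of -1 it was 75%, 78%, 85%, so there the scale contributed more than the adjustment. Z-scores taken from rounded percentiles capped at the 1st and 99th still beat percentiles under the same adjustment in every scenario.

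**The case against.** The strongest defence is that the outcome definition, power statement and Table 2 all agree on percentile, and that standard scores may be loose wording covering four instruments. A t-test on percentile change is a valid comparison of randomized groups. Aim 2 inherits the Aim 1 follow-up regression, which includes baseline, and motor effects are also examined on PDMS-2 scaled scores. An inverse-normal transform adds no information, assumes normality, needs a cap and stretches small percentile differences in the tails.

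Much of this stands and limits the point. A reader might infer three stronger things that the documents do not support:

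- **That the primary test is biased or the 23 points uninterpretable.** It is not biased, and 23 points is well defined on its own scale. What it lacks is a constant SD equivalent and a stated SD.
- **That power is seriously reduced because delay is common.** The Background statement "Delays in motor, language, and social development affect 75% of boys with XXY" covers three domains and boys generally. It does not give AIMS positions at 4-12 weeks of age. The implied SD near 30 also argues against a cohort deep in the lower tail, though that inference rests on an assumed model and a pilot of 18 infants.
- **That %BF is expressed as a z-score to avoid this problem.** The plan says only that z-scores come from published age norms.

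The defence does not remove the conflict in wording, the missing SD or the absence of baseline from the primary test. The adjusted regression comes second.

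**Conclusion.** The point holds as a matter of scale, efficiency and interpretation, not validity. The plan names two scales for one primary outcome, and its detectable difference corresponds to about 0.6 SD of motor gain from the middle of the distribution and 1.1 SD from the 5th percentile.

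The percentile scale alone costs about 0 to 7 points of power for cohort means of 0 to -1 SD. The cost reaches 5 to 18 points only at a mean of -2 SD, where nothing in the documents places these infants. Leaving baseline out of the primary test generally costs more than the scale does for cohort means of 0 to -1 SD. All power figures rest on normal z-scores, a constant shift in z, correlations of 0.3 to 0.7 and 27 per arm.

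**What to change.** - Make the Aim 2 primary analysis a comparison of 12-week AIMS z-score between arms, with baseline AIMS z-score as covariate. Define the z-score as the inverse-normal of the age percentile, with a prespecified cap such as the 1st and 99th percentiles. This needs only the percentile already planned; the documents do not say whether an age-normed AIMS standard score is available.
- Use that one scale in the Aim 2 hypothesis (section I), the outcome list (IV.A), the Aim 2 analysis and power text (IV.F) and Table 2.
- State the pilot SD and the number of infants behind it, and give the detectable difference in SD units.
- Report percentiles descriptively.

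The cost is a transformation and wording, settled before unblinding, with no new data or visits. The downsides are that z-scores are less familiar to clinicians, which the descriptive percentiles cover, and that the cap is a convention. A sensitivity analysis with a different cap would show whether it matters.

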### B. Description of Population to be Enrolled:

A total of 75 infants with XXY will be enrolled. We will include all races, ethnicities, and languages.

*Inclusion criteria:* Male infants with 47,XXY karyotype identified prenatally who are 4-12 weeks old (31 to 90 days of age). 47,XXY must be from a diagnostic test such as CVS, amniocentesis, or post-natal blood/tissue. Non-invasive prenatal screening results alone will not be accepted.

*Exclusion criteria:*

- 1) >20% mosaicism for a normal cell line
- 2) Gestational age at birth <36 weeks
- 3) Birth weight <2.5thile or >97.5thile for age (small or large for gestational age)
- 4) History of thrombosis in self or a first degree relative
- 5) Exposure to androgen therapy outside the study protocol
- 6) Use of medications known to affect body composition, such as growth hormone or insulin
- 7) Known allergy to the testosterone cypionate solution components including benyl benzoate, benzyl alcohol, or cottonseed oil

Involving children is imperative as boys <18 years of age with XXY are much a different population than adult men with XXY. Men with XXY have been shown to have a high prevalence of type 2 diabetes, metabolic syndrome, fatty liver disease, and psychosocial difficulties. Clearly these processes begin in childhood. The potential to intervene in a preventative fashion, prior to the onset of disease, is more promising and productive than trying to treat pre-existing disease. Infant boys are exposed to endogenous testosterone in the first few months of life known as the “mini-puberty period of infancy.” Animal and human studies suggest this is a critical period for biologic programming, and therefore cannot be replicated at any other point in life. Including children in this study design allows us to investigate testosterone as a targeted intervention at this critical time point with evaluation of early markers of disease and disability. The ultimate goal is to improve the lives of children and adults with this condition.

The age of the infants at enrollment was chosen 1) to allow assessment of testicular function during the expected mini-puberty period of infancy, 2) to assure visits 2 and 3 will be completed before the infant is 10kg, as this is the upper weight limit for the PeaPod (our body composition assessment tool), and 3) feedback from parents.

### C. Study Design and Research Methods

**Overall study design.** TESTO is a randomized controlled trial assessing the efficacy and safety of T injections in infants with a prenatal diagnosis of XXY. Body composition, neurodevelopment, serum hormones, safety parameters, and metabolomics will be assessed at baseline, 12 and 24 weeks into the

study. Infants will be randomized 1:1 to receive T vs placebo for the first 12 weeks of the study with the primary outcomes assessed after 12 weeks (Figure 5). The second half of the study will cross the treatment groups allowing us to evaluate if timing makes a difference in response and if initial benefits are sustained. This plan will optimize enrollment, as many parents will only participate if their son will get treatment, and allow us to maintain the blinded design.

**Setting.** The study will be conducted at Children’s Hospital Colorado (CHCO) in the outpatient Pediatric Clinical Translational Research Center (CTRC). CHCO is home to the eXtraordinary Kids Clinic, the first comprehensive interdisciplinary clinic for sex chromosome aneuploidies. The unique collaborative model and our expertise has led to national referrals and a high demand for clinical evaluations. We have successfully recruited hundreds of boys with XXY to participate in longitudinal and interventional research studies through close collaboration with family support groups and national/international experts in XXY. Our investigative team has expertise in child development, infant body composition, childhood disorders of insulin resistance, metabolomics, clinical trial recruitment, robust data acquisition and data analysis, making this the ideal setting.

[figure not shown]

Figure 5. Overall Study Design

**Recruitment and Retention.** Methods of recruitment will include 1) approaching new and existing patients seen at CHCO clinics including the eXtraordinary Kids Clinic, Genetics Clinic, and Endocrinology Clinics, 2) outreach to the genetic counselors and obstetricians in the Denver metropolitan area who are ordering and interpreting prenatal testing results, 3) genetic counselors at CHCO who may receive calls/referrals for infants with XXY diagnoses, 4) Email and mailings to pediatric endocrinologists around the country (existing listserv) and through posting on the Pediatric Endocrinology Society active research website, 5) advertisements through the parent support group AXYS including websites, social media, emails, flyers, and mailings, 6) Email and mailings to prenatal genetic counselors throughout the country (existing listserv), and 7) study information on websites including Clinical Trials .gov, University of Colorado and Children’s Hospital of Colorado. To facilitate dissemination of information about our study, we will design study-specific webpage linked off the existing eXtraordinary Kids website.

The goal for recruitment will be 15 subjects per year in years 1-4. Based on our pilot study this goal is easily achievable. Modest travel expenses will be covered for out-of-state participants.

In between study visits, families may receive newsletters from the eXtraordinary Kids Clinic with updates from our ongoing research and periodic phone calls to stay in touch. Families will be invited to our eXtraordinary Party in conjunction with the bi-annual AXYS family conference.

**Enrollment in multiple clinical trials.** Enrollment in this protocol does not exclude participation in other clinical studies, with the exception of studies involving an intervention of androgen and/or other treatment that may impact body composition. Our team is concurrently enrolling for other studies involving infants with XXY, including the eXtraordinary Babies Study (COMIRB 17-0118). These studies are complementary and participants can enroll in either or both studies. If participants enroll in both studies, visits will be coordinated for convenience of the participant’s family and duplicate measures (ie blood draw, developmental testing, etc) will be combined.

**Consent.** When a child is identified through clinic or other method identified above, a member of the study team will contact the parent to inform them of the opportunity to participate in a study. In many cases, the parents will contact the PI, PRA or genetic counselor of the eXtraordinary Kids Clinic after hearing about the study from one of the above sources. Prior to any information being collected, verbal consent to ask questions pertaining to the inclusion/exclusion criteria will be obtained. A member of the study team will describe the study and will offer to email/mail the consent form to the parents so the parents have ample time to review prior to deciding whether to schedule the first visit and enroll in the study.

Prior to any research procedures being performed, a study team member will review the consent form in person in a private location. Both verbal and written consent will be required from a parent or legal guardian to enroll in the study. All of the subjects in this protocol are infants and therefore too young to assent/consent to research participation themselves. To minimize coercion, parents will not be paid for enrolling their child in the study and only reimbursement for reasonable travel will be provided. We will emphasize to parents their child's participation is entirely voluntary and can be withdrawn at any time. As part of the consent process, parents will be asked to summarize the study in their own words to ensure comprehension, and parents will have the opportunity to ask questions. If the consenting parent does not speak English, an interpreter will assist with the consent process and a short-form consent document in the parent's preferred language will be completed. If the consenting parent is blind, illiterate, or with reading limitations, the entire consent form will be read to the subject and witnessed by someone outside of the study team.

**Randomization.** Subjects will be randomized 1:1 using block randomization in groups of 20 to 1) receive T treatment in the first 12 weeks followed by placebo, or 2) placebo for the first 12 weeks followed by T. Investigational Drug Services at CHCO will generate the automated randomization list and dispense the study drug to maintain allocation concealment. All investigators and parents will remain blind to the intervention group.

